5.1.15 PFS Follow-up Procedures

Because the primary endpoint of the study is PFS, patients who are taken off treatment for any reason other than disease progression will REMAIN ON PROTOCOL and continue with the protocol mandated schedule of events (i.e. staging studies) until progressive disease, start of new anti-cancer therapy, or death, whichever comes first. For example, patients who are randomized to Arm B (fulvestrant + ganetespib) and who discontinue ganetespib without evidence of progression should continue on fulvestrant alone and continued to be followed for progression with staging studies/evaluations per protocol.

5.1.16 Survival Follow-up Procedures

Subject survival information will be collected every 3 months (+/- 2 weeks) from date of last dose of study drug (first treatment they were assigned to) until the subject's death, or until the subject is lost to follow-up, or up to 2 years from last dose of study drug, whichever comes first.

For patients who receive post-protocol care at a participating institution, survival information will be collected from medical records, supplemented by direct contact with a patient's treating physician. Patients who receive post-protocol care outside of a participating institution will be directly contacted by telephone. If a patient or patient representative is not able to be successfully contacted, then the patient's local physician will be contacted as an alternative. Prior to deeming a patient lost to follow-up, a search will also be made of the Social Security Death Index and/or the National Death Index. At the time of final survival reporting, any patients with missing survival data will also be searched through the Social Security Death Index and/or the National Death Index. The consent form will include information detailing the follow up procedures in this trial. The following information will be collected:

- The subject's survival status, and if deceased, the date of death.
- The method by which the survival status was assessed and the date it was assessed.
- The cause of death, if known
- Categorization of cause of death, if known (e.g. disease progression, protocol-related toxicity, other treatment-related toxicity, other, or unknown).

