5.8 Duration of Survival and Adverse Event Follow Up

Participants will be followed for survival for up to 4 years after the last dose of protocol therapy or until death, whichever occurs first. Participants removed from study for unacceptable adverse events will be followed until resolution or stabilization of the adverse event.

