5.9 Criteria for Removal from Study

Participants will be removed from study treatment when any of the following occur:

CONFIDENTIAL

This document is confidential. Do not disclose or use except as authorized.

- Disease progression,
- Start of new anti-cancer therapy, or
- Participant decides to withdraw from the study treatment
- Subject death

Note: Patients in Arm A who progress on fulvestrant alone may first cross over to Arm C (fulvestrant + ganetespib).

Participants will be considered ‘Off Study’ when one of the following events occurs:

- Death
- Participant decides to withdraw from the study follow-up procedures
- 4 years after the date of the last study treatment dose

Note: Patients on either arm who discontinue assigned protocol treatment (fulvestrant and/or ganetespib) for any reason other than progression or death *should not be removed from study but instead should continue to be followed per protocol (See Study Calendar D) until evidence of disease progression, start of new anti-cancer therapy, withdrawal of consent for follow-up, or death, whichever occurs first.*

The reason for study removal and the date the participant was removed must be documented in the study-specific case report form (CRF). Alternative care options will be discussed with the participant.

In the event of unusual or life-threatening complications, participating investigators must immediately notify the Principal Investigator (or Protocol Chair), [name] at [contact], [name].

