10.1.9 Overall Survival

Overall survival is defined as duration of time from start of treatment to death due to any cause, or censored on the date last known alive.

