14.4 Analysis of Secondary Clinical Endpoints

Safety and toxicity: All patients who received at least one dose of protocol therapy (fulvestrant, ganetespib, or both) will be included in the safety/toxicity analysis. Toxicity will be graded according to NCI CTCAE, Version 4.0. The proportion of patients who experience each type and grade of toxicity will be presented in tabular form. Toxicity will be described separately in Arm A (pre-crossover), Arm C (post-crossover), and Arm B.

Objective Response Rate: All patients with measurable disease at baseline will be included in the analysis of response rate. Response will be assessed using RECIST 1.1, as described in Section 10. The response rate will be calculated separately in Arms A, B, and C. Response rates in Arm A and Arm B will be compared using a one-sided Fisher exact test. An intent to treat analysis will be used, so all patients randomized in the measurable disease stratum will be used in the

analysis; patients with no follow-up response evaluation will be assumed to be non-responders. Assuming that 57 patients are entered in the measurable disease stratum, there will be 81% power to decide that the ganetespib arm has a better response rate if the true response rates on the two arms are as different as 36% and 5%, or 44% and 10%.

Clinical benefit rate: Clinical benefit will be defined as CR + PR + SD \geq 6 months. All patients will be included in the analysis of clinical benefit. CBR will be calculated separately in Arms A and B, and compared using a one-sided Fisher exact test. All patients randomized on study will be used in this analysis, and patients with no follow-up response evaluation will be assumed not to have clinical benefit. With 71 patients randomized, there will be 80% power to decide that the ganetespib arm has a better clinical benefit rate if the true benefit rates on the two arms are as different as 63% and 30%, or 73% and 40%.

Overall survival: Overall survival is defined as duration of time from randomization to death due to any cause, or censored on the date last known alive. All randomized patients will be included in the analysis of OS. OS will be estimated separately in Arm A and Arm B. OS will be analyzed at the same time as the final analysis of PFS, although it is acknowledged that the percent of survival censoring at that time will be larger than the percent of PFS censoring, and this will limit the power to detect survival differences between the arms.

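### OS counts death-index deaths up to the search date but censors unmatched patients at the date last known alive, which biases survival modestly downward

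*Combined protocol and SAP*

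**What the plan says.** Section 5.1.16 collects survival status every 3 months, counted "from date of last dose of study drug (first treatment they were assigned to", until death, loss to follow-up, "or up to 2 years from last dose of study drug, whichever comes first". The death indexes are searched before a patient is declared lost. At final reporting "any patients with missing survival data will also be searched through the Social Security Death Index and/or the National Death Index". The date and method of each status assessment are recorded.

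Section 14.4 measures OS from randomization to death from any cause, "or censored on the date last known alive". Section 10.1.9 has the same censoring rule but starts OS at the start of treatment. OS is analysed together with the final PFS analysis.

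The length of survival follow-up is stated differently elsewhere. Section 5.8 says "Participants will be followed for survival for up to 4 years after the last dose of protocol therapy", and section 5.9 takes a participant off study "4 years after the date of the last study treatment dose". The survival-status rows of Study Calendars A to D refer to 5.1.16.

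**The concern.** A patient whose status is missing has two possible endings. If the index shows a death, the death enters at its true date, possibly long after the last contact. If the index shows nothing, the patient leaves the risk set back at the last contact. Time after last contact can therefore contribute deaths but no survival time. That is informative censoring, and it lowers the Kaplan-Meier curve.

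Section 1.3 makes describing and comparing OS between arms a secondary objective. With 24 and 47 patients, readers will look at the curves, medians and landmark rates, and those are what move. If the arms also differed in how early contact stops, the distortion could differ by arm.

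**Working it through.** **The plan's own figure.** The documents give no power or precision figure for OS, so the timing inputs were checked against the PFS calculation in 14.2: 20 and 40 effective patients, medians 4 and 8 months, accrual A = 20 months, further follow-up F = 20 months. With λ = ln 2/median, expected events per arm are n[1 − (e^(−λF) − e^(−λ(A+F)))/(λA)]. This gives 19.8 + 36.6 = 56.5 (stated: 57). Power is Φ(√(56.5 × 1/3 × 2/3) × ln 2 − 1.645) = 0.79 (stated: 80%). The timing reproduces.

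**Inputs for OS.**
- Analysis at month 40 and uniform accrual over 20 months (14.2), so potential follow-up is 20 to 40 months, average 30.
- Median time on first treatment 4 months (A) and 8 months (B), taking the PFS medians of 14.2 as a proxy.
- Assumption: true OS is exponential and equal in both arms, median 24 or 36 months. Section 2.3 gives approximately 3 years as background.
- Assumption: 15% lost, at a uniform time. Section 14.2 gives 15% for PFS censoring, which includes new anti-cancer therapy.
- Assumption: the index captures every death.

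**Hand check, 4-year window.** The earliest window closes at month 48, after the month-40 analysis, so only lost patients matter. All deaths are counted, but the time from last contact to the analysis is dropped for lost patients still alive. Hence apparent death rate/true rate = T/(T − omitted), with T the full person-time per patient. At the average follow-up of 30 months:
- Median 36: λ = 0.01925, S(30) = 0.561, T ≈ (1 − 0.561)/0.01925 = 22.8 months, omitted ≈ 0.15 × 0.561 × 15 = 1.26 months. Ratio 22.8/21.5 = 1.06.
- Median 24: λ = 0.02888, S(30) = 0.420, T ≈ 20.1, omitted ≈ 0.15 × 0.420 × 15 = 0.95. Ratio 20.1/19.1 = 1.05.

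**Simulation** (400,000 per arm, contact continuous until it ends). In the 4-year, 15%-lost case, OS falls as follows, within 0.001 of the same value in both arms:
- Median 24: 0.500 to 0.484 at 24 months, 0.420 to 0.399 at 30, 0.354 to 0.329 at 36.
- Median 36: 0.630 to 0.616, 0.561 to 0.540, 0.500 to 0.474.

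A separate run at median 36 with 3-monthly contacts and slightly fewer losses in Arm B gave shortfalls of 1.3 to 2.8 points in A and 0.9 to 1.9 in B.

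36-month OS under each reading:

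| Follow-up window and who is searched | Median 24, truth 0.354: A, B | Median 36, truth 0.500: A, B |
|---|---|---|
| 4 years, nobody lost | 0.354, 0.354 | 0.50, 0.50 |
| 4 years, 15% lost and searched | 0.329, 0.329 | 0.474, 0.473 |
| 2 years from first assigned treatment, 15% lost, only they are searched | 0.288, 0.317 | 0.432, 0.458 |
| 2 years from first assigned treatment, nobody lost, everyone past the window searched | 0.204, 0.286 | 0.329, 0.428 |
| As the row above, with Arm C time (assumed median 4 months) extending Arm A's window | 0.304, 0.286 | 0.447, 0.428 |

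In the fourth row 1.3% to 1.6% of Arm A (at most 0.016 × 24 = 0.4 patients) and 2.7% to 3.8% of Arm B (at most 0.038 × 47 = 1.8 patients) are still at risk at 36 months. At 24 months both arms are unbiased in that row.

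**With the fix.** Censoring searched, unmatched patients at the common cut-off returns both arms to the truth in the second, fourth and fifth rows.

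**The case against.** The best defence is that the censoring rule refers to the date last known alive, not the last contact, and 5.1.16 records the method and date of every status assessment. An analyst could treat a negative search as an assessment and censor at its date. That is a sensible practice, but the plan does not state it. A negative search does not in itself establish that someone is alive, and no sentence links the assessment date to censoring.

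It is also fair that OS is secondary, that 14.4 already concedes limited power for it, and that the effect on the overall death rate is small. These points limit the importance of the problem but do not remove it.

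Two stronger readings are tempting. The first is that the survival clock starts at the end of the first assigned treatment. It does not: 14.4 and 10.1.9 start OS at randomization or start of treatment, and only the contact schedule in 5.1.16 is tied to that last dose.

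The second is that the plan manufactures an 8 to 10 point survival advantage for ganetespib. That needs four things together: the 2-year limit overrides 5.8 and 5.9; it runs from the first assigned treatment, although the parenthesis in 5.1.16 may qualify only when contact begins; patients who completed it count as having missing data, which is undefined; and first treatment is shorter in Arm A. The references from the calendars to 5.1.16 make the 2-year limit a possible reading, but no more than that. If Arm C time extends Arm A's window, the gap slightly reverses.

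**Conclusion.** The asymmetric follow-up is real, and no rule in the documents corrects it. Under the 4-year window with 15% lost and searched, OS at 24 to 36 months is about 1.5 to 3 points too low, with little difference between arms. The bias is roughly proportional to the loss rate, so at 5% lost it would be about 0.5 to 1 point, and with nobody lost it is zero.

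The arm-dependent tail effect (36-month OS 8 to 10 points lower in Arm A than in Arm B) is conditional and sits where about 1% to 4% of patients remain at risk. It is a reason to settle the wording, not evidence of a false treatment effect. Even with the 2-year window, everyone out of contact searched and 15% lost, the spurious B/A death-rate ratio is only about 0.96 to 0.97.

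All sizes rest on the assumed OS medians, loss rate, exponential times and complete index capture. The point is worth correcting because the correction is cheap, not because the bias is large.

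**What to change.** In 10.1.9 and 14.4, set one OS cut-off date for all patients. Censor a patient with a negative index search at the earlier of that cut-off and the date through which the index is complete, and count index deaths only up to the same date. Define which patients have missing survival data, in particular whether those who completed the contact period are included.

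Reconcile the survival follow-up window in 5.1.16 (2 years, first assigned treatment) with 5.8 and 5.9 (4 years, last protocol or study treatment), so that one rule applies in both arms. Removing the parenthesis from 5.1.16 is not enough, because 2 years against 4 years would remain. Reconcile the OS starting point between 10.1.9 (start of treatment) and 14.4 (randomization).

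The cost is a few sentences, since the index search is already planned. The one downside is that a death the index fails to match is counted as survival to the censoring date, a small bias in the other direction.

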5.2 Agent Administration

5.2.1 Ganetespib

- Administration -- 200 mg/m² IV D1, 8, 15 of a 28-day cycle (i.e. 3 weeks on, 1 week off)
- Ganetespib should be infused over 1 hour using non-PVC, non-DEHP IV bags and tubing with a 0.2µm in-line filter.
- Based on preclinical data, use of vascular access devices (VADs) (such as ports and peripherally-inserted central catheters [PICCS]) containing silicone catheters or peripheral IV is permitted. ***Use of VADs with catheters made of any other material***

CONFIDENTIAL

This document is confidential. Do not disclose or use except as authorized.

is not permitted. Following ganetespib administration through a VAD, care should be taken to flush the line after each dose of study drug.

- For patients with a pre-existing port: Prior to the first ganetespib administration, the treating investigator must send the name of the port device to the overall study PI and Coordinating Center contact and the overall study PI and/or her designate must approve the device prior to use for ganetespib administration.
- For patients who will have a port placed during the study: prior to port placement, the treating investigator must send the name of the intended port device to the overall study PI and Coordinating Center contact and the overall study PI and/or her designate must approve the device prior to the insertion procedure.
- Premedications:
 - Dexamethasone 10 mg IV, or therapeutic equivalents (**Required**)
 - Diphenhydramine HCL 25-50 mg, or therapeutic equivalents (**Required**)
 - *Dose of diphenhydramine may be reduced per investigator discretion if patient experienced previous problems with 25mg or higher*
 - Loperamide (Imodiu^{m®}): Start dosing (2mg) 1-2 hours **before** ganetespib infusion (Suggested)
 - *For patients who have successfully tolerated at least 2 cycles of ganetespib without a hypersensitivity reaction, routine premedication with dexamethasone and diphenhydramine prior to subsequent ganetespib infusions is not required and is left to the discretion of the treating provider.*
- No pre- or post-hydration is required
- Dose modifications are outlined in Section 6

5.2.2 Fulvestrant

- Administration – 250 mg/5mL (x2) for a total of 500 mg via intramuscular injection on Cycle 1 Day 1, Cycle 1 Day 15, and then on Day 1 of each subsequent cycle.
- No dose modifications.
- Commercial supply of fulvestrant will be used.

5.3 Definition of Dose-Limiting Toxicity

There are no phase I data with the combination of fulvestrant + ganetespib. Based upon the observed toxicities to date, mechanism of action, and metabolisms, no additive toxicities are anticipated. However, for the first 10 patients assigned to Arm B, we will include an early stopping rule for Cycle 1 dose-limiting toxicity (DLT). The DLT assessment period will be from Cycle 1 Day 1 until Cycle 2 Day 1.

Dose-limiting toxicity (DLT) is based on the CTEP Active Version of the NCI Common Terminology Criteria for Adverse Events (CTCAE v4.0). DLT refers to toxicities experienced during the first cycle of treatment. A DLT will be defined as follows:

- Grade 3 or 4 hematologic or non-hematologic toxicity thought likely or definitely related to protocol therapy will be counted as a DLT, with the exception of:
 - Grade 3 diarrhea that responds to maximal supportive measures. If grade 3 diarrhea is persistent > 7 days despite maximal supportive measures, it will be counted as a DLT
 - Grade 3 fatigue
 - Grade 3 hot flashes
 - Grade 3 electrolyte disturbance, unless persistent for > 7 days despite maximal supportive measures.

Management and dose modifications associated with the above adverse events are outlined in Sections 5.4 (General Concomitant Medication and Supportive Care Guidelines) and Section 6 (Expected Toxicities and Dosing Delays/Dose Modifications).

5.4 General Concomitant Medication and Supportive Care Guidelines

Medications taken prior to Cycle 1, Day 1 and during the study will be collected and noted in the medical record. The following are the supportive care guidelines for the study. The guidelines apply to all Arms of the study, except as otherwise noted:

- For patients receiving ganetespib, it is preferred not to use concomitant use of medications that are associated with a high incidence of QT prolongation (e.g., quinolones and ondansetron). See Appendix I for a list of medications that are known to predispose to Torsades de Pointes.
- No other antineoplastic agents will be permitted during this study, with the exception of bisphosphonates and GnRH agonists under the guidelines as specified in Section 3.1.8 and 3.1.10.
- No concurrent radiation treatment will be permitted during this study
- No treatment with chronic immunosuppressants (e.g., cyclosporine following transplantation or systemic steroids for treatment of autoimmune disease) will be permitted during this study; however, use of inhalant steroids and steroids given for antiemetic purposes are permitted
- For patients receiving ganetespib, caution should be exercised when concomitant medications that are cleared predominantly by the CYP3A4 or CYP2C19 pathways are administered. Examples of compound classes metabolized predominantly by CYP3A4 or CYP2C19 are provided below:
 - CYP3A4 substrates: benzodiazepines (e.g. midazolam), anticonvulsants (e.g. carbamazepine), calcium channel blockers (e.g. felodipine, nifedipine), antineoplastics (e.g. vincristine), macrolide antibiotics (e.g. erythromycin) and HIV antiviral agents.
 - CYP2C19 substrates: proton pump inhibitors (e.g. omeprazole) and antidepressants (e.g. sertraline).

The above information is precautionary only. Investigators are encouraged to discuss the use of individual medications with the Principal Investigator on a case-by-case basis.

CONFIDENTIAL

This document is confidential. Do not disclose or use except as authorized.

5.5 Supportive Care Guidelines

Patients should receive full supportive care, including antiemetics, blood transfusions, intravenous fluid, etc., as clinically appropriate. The reason(s) for treatment, dosage, and dates of treatment should be recorded in the medical record.

Antiemetics

Patients may be given antiemetics at the discretion of the treating physician.

Anti-infectives

Antibiotics may be used at the discretion of the treating physician. If there is a reasonable alternative, it is preferred that quinolones and other agents that may prolong QTc are avoided.

Bisphosphonates

Oral or intravenous bisphosphonate treatment is allowed if the first dose was given prior to initiation of protocol therapy. Patients already receiving bisphosphonate therapy at the time of study entry may continue the treatment. Patients with new bone metastases documented as part of study screening procedures may begin a bisphosphonate, provided the first dose is given prior to initiation of protocol-based therapy. Bisphosphonates may not be started after the initiation of protocol-based therapy.

Growth factors

Patients may receive erythropoietin or other specific red blood cell growth factors and red blood cell transfusions will be permitted as clinically indicated during the study.

Patients may receive bone marrow colony stimulating factors (such as granulocyte colony-stimulating factor or granulocyte-macrophage colony-stimulating factor) as clinically indicated during the study.

If an Investigator determines a patient is at risk for severe neutropenia or febrile neutropenia, granulocyte-colony stimulating factor (G-CSF) may be used prophylactically beginning with the first cycle. G-CSF prophylactic use is recommended during subsequent treatment cycles in case of neutropenia lasting more than 7 days, febrile neutropenia, or documented infection with neutropenia.

Diarrhea management guidelines

Many patients will experience diarrhea, and some patients may experience Grade 3 or 4 diarrhea. The following proactive and ongoing management principles are necessary to avoid more serious complications of diarrhea. However, guidelines such as these should never replace sound clinical judgment.

Experience suggests that diarrhea is an expected drug class effect for Hsp90 inhibitors and it typically starts 2-3 hours following administration of ganetespib in most patients. However,

CONFIDENTIAL

This document is confidential. Do not disclose or use except as authorized.

when appropriately managed with anti-diarrhea treatment, it is generally mild to moderate and its duration limited to 24 hours.

Due to the risk of diarrhea while receiving ganetespib, all patients will be educated to use prophylactic medication (Lomotil® or Imodium®) before ganetespib administration and before the onset of gastrointestinal symptoms to mitigate the severity and duration.

Suggested prophylaxis regimens are as follows:

- Loperamide (Imodium®): Start dosing (2mg) 1-2 hours **before** ganetespib infusion and continue with 2 mg every four hours for 12 hours. This treatment may be continued for up to 24 hours in the absence of symptoms of diarrhea. Due to inter-patient variability, adjustment to this regimen should be made on a case-by-case basis. The maximum dosage of loperamide is 16 mg/24 hrs.
- Dietary counseling: foods/liquids and quantities to intake or avoid

Guidelines for Treatment of Diarrhea (Active Management):

- In the event of diarrhea, patients will take loperamide at an initial 4 mg dose followed by 2 mg doses every 4 hours. In the presence of uncomplicated grade 1 or 2 diarrhea, loperamide will be continued until the patient is free from diarrhea for 12 hours. Total daily dose may not exceed 16 mg (8 capsules)
- If mild to moderate diarrhea persists after 24 hours despite treatment with loperamide, a cocktail of atropine-diphenoxylate (lomotil) or equivalent and loperamide may be considered. Loperamide 2 mg may be alternated with one tablet of Lomotil every 3 hours.
- For grade 3 or 4 diarrhea or complicated grade 1 or 2 (severe cramping, severe nausea/vomiting, decreased PS, fever, sepsis, grade 3 or 4 neutropenia, frank bleeding, dehydration), IV fluids will be used as appropriate, as well as prophylactic antibiotics. Hospitalization is recommended.
- Grade 1-2 : Loperamide 4mg first dose, then 2 mg every 4 hours until free from diarrhea for 12 hours
- If Grade 1 or 2 diarrhea persists for more than 24 hours: Loperamide 2mg q 2 hrs
- If Grade 1 or 2 diarrhea persists after 48 hours: Start 2L agents: a cocktail of Dyphenoxylate and atropine sulfate (Lomotil®). Alternate 2 mg loperamide with one tablet of Lomotil every 3 hours.
- Grade 3 or 4 or Complicated Grade 1 or 2: IV fluids as appropriate.

Management of hypersensitivity reactions

Ganetespib contains a surfactant (polysorbate 80) that has been associated with hypersensitivity reactions in other medications administered by infusion. Infusion type reactions associated with ganetespib (approximately 7% of patients) have been reported at doses of 10 to 200 mg/m². Symptoms included pruritus, flushing, shortness of breath, chest tightness, dizziness, headache, increased systolic blood pressure and heart rate. These events were mostly grade 1 and grade 2 and usually responsive to treatment with i.v. diphenhydramine HCl (Benadryl®) and steroids

CONFIDENTIAL

This document is confidential. Do not disclose or use except as authorized.

(sometimes with H2 blockers). In addition, subjects with infusion-type reactions usually could continue receiving ganetespib after pre-mediation with diphenhydramine HCl and steroids.

Based on IB Edition 9, premedication is required prior to ganetespib infusion for at least 2 cycles. Premedications include:

- Dexamethasone 10 mg IV, or therapeutic equivalents
- Diphenhydramine HCl 25-50 mg, or therapeutic equivalents
 - *Dose of diphenhydramine may be reduced per investigator discretion if patient experienced previous problems with 25mg or higher*

For patients who have successfully tolerated at least 2 cycles of ganetespib without a hypersensitivity reaction, routine premedication with dexamethasone and diphenhydramine prior to subsequent ganetespib infusions is not required and is left to the discretion of the treating provider.

If, despite premedication, an infusion hypersensitivity reaction to ganetespib is suspected, the following management is provided as guidance only; treatment will be based on clinical presentation. Institution specific premedication and/or treatment procedures and regimens may also be appropriate in lieu of these guidelines.

- **Mild and moderate symptoms:**

1. Stop ganetespib administration
2. Give i.v. diphenhydramine HCl (Benadryl[®]) 25-50 mg and dexamethasone 10 mg i.v.
3. After recovery from symptoms, resume ganetespib infusion or re-schedule patient for re-treatment; a reduced flow rate may be considered

In subsequent cycles, consider optimizing premedication regimen.

- **Severe symptoms** (i.e., hypotension requiring pressor therapy, IV fluids, angioedema, respiratory distress requiring bronchodilator therapy, generalized urticaria):

1. Stop ganetespib administration
2. Give intravenous dexamethasone and diphenhydramine HCl (Benadryl[®]) as above
3. Add intravenous H2 blocker
4. Add adrenaline (1:1000) or bronchodilators as indicated
5. Reschedule dose administration for the following day
6. In subsequent cycles, consider optimizing premedication regimen.

If severe symptoms reoccur with optimal premedication, treatment with ganetespib should be discontinued permanently.

The following is an example of an optimized premedication regimen:

CONFIDENTIAL

This document is confidential. Do not disclose or use except as authorized.

- Dexamethasone 12 mg PO and diphenhydramine HCL 25-50 mg PO approximately 12-24 hours prior to the next dose of ganetespib
- Repeat dexamethasone 12 mg PO and diphenhydramine HCL 25-50 mg PO approximately 4-6 hours prior to the re-challenge

